#### 9.2 Computational methods

Standard software for frequentist methods will be used, such as SAS or STATA.

#### 10. Miscellaneous features of the SAP

#### 10.1 Data checking

Data collection forms will be pseudonymised with the use of a study-specific unique identifier, and data entered into a REDCap (Research Electronic Data Capture) database. Within REDCap, a comprehensive set of data quality checks will be conducted periodically to cross-validate the entire patient record. These will include validation checks (including data type; range), cardinality, consistency checks and logic checks. Data queries and source data verification requests will be generated and relayed back to each participating site, with all changes to data during the cleaning process documented.

#### 10.2 Missing data

With so many variables, and with so many different analyses, it is difficult to make any general comments on methods for handling missing data. The following comments set out our general approach:

1. In the case of diagnostic test variables, the concept of "missing data" is not applicable: for the purposes of determining whether mothers have been infected in pregnancy, and if so when, the methods are designed to deal with any pattern of test results occurring at any time before, during, and after pregnancy, including no tests at all. A probability distribution will be created for every woman reflecting when maternal infection took place and whether it took place. With regards to vertical infection, the analysis will assign every child a probability of being vertically

Author: [name] (UNIVBRIS)

31

infected, based on test results, which will be 0,1, or a probability determined by the duration of antibody persistence when last tested.

- 2. With regards to explanatory variables, all analyses will be based on a "complete data" analysis, which assumes that data is missing without regard to outcomes.
- 3. Loss to follow-up will be carefully monitored and tabulated in relation to infection status, in both pediatric and maternal follow-up studies.
- 4. For categorical pediatric outcomes, survival analyses will treat loss to follow-up as censored observations. Alongside these analyses, sensitivity to assumptions about informative censoring will be carried out, including examination of the most extreme assumptions, in which (a) all, or (b) no, censored observations are assumed to reach the endpoint

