### 3. Relation to ZIKA-PED, ZIKA-VID and ZIKA-SYN

#### 3.1 Outcomes of postnatal pediatric infection: ZIKA-PED.

Follow-up of postnatal infections, both primary and secondary, are within the remit of ZIKA-PED. However, postnatal infection will also be observed in ZIKA-VT. The statistical analysis of clinical symptoms and outcomes following postnatal infection seen in ZIKA-VT will be considered as part of the main ZIKA-PED analysis. However, estimation of post-natal ZIKV incidence rates in the control groups, part of ZIKA-PED, may be used to assist in the analysis of vertical transmission rates (see below and *Appendix 5*).

By the same token, after the two-year follow-up specified in ZIKA-VT, further follow-up of the three ZIKA-VT birth cohorts – Vertically Infected (VI), Maternal Infection no VI (MI – No VI), and No Maternal Infection (No MI) – will be undertaken within ZIKA-PED. However, to answer the scientific questions about outcomes of vertical infection, the statistical analysis of outcomes of vertical transmission after 2 years will be regarded as being within the remit of the ZIKA-VT statistical analysis plan. The ZIKA-PED (prospective) SAP will focus on outcomes of post-natally acquired ZIKV, which will be observed in the MI-No VI and No MI cohorts.

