#### 5.2 Numerator for VTR

Fetuses will be regarded as vertically infected if fetal or placental tissue, or amniotic fluid, tests PCR+. Children will be regarded as vertically infected on the basis of IgM or PCR evidence within 7 days of delivery. Infants who lose antibody will be regarded as not vertically infected: this includes infants in whom a falling IgG titer is observed as well as those who become IgG-.

There are reports of children with clinical signs of congenital infection, such as microcephaly, whose mothers were infected in pregnancy, but in whom no laboratory evidence of congenital ZIKV can be obtained from testing serum and CSF for IgM and PCR. Definitions of congenital zika in the absence of laboratory evidence are being developed [2, 3], which may be revised as new data becomes available. Although the evidence is not clear at the time of writing, it seems likely that these infected children will remain IgG antibody positive.

Infants who are IgG antibody positive when last seen may be congenitally infected. The probability that they are congenitally infected depends on two factors: firstly, their age, because maternal antibody declines over time and is usually absent within 15 months. Secondly, the risk of post-natal

Author: [name] (UNIVBRIS)

15

infection. Appendix 5 describes statistical analyses that use data on antibody loss in control children born to IgG+ mothers, and data on post-natal infection on initially IgG- newborns, to estimate the probability of vertical infection in all IgG+ infants whose infection status cannot otherwise be determined.

It remains possible either that congenital infection can take place, causing damage, and clearing prior to delivery and leaving no laboratory markers; or that maternal infection affects fetal development without crossing the placenta. It is for this reason that ZIKA-VT includes a 2nd control group, of children born to mothers with no infection in pregnancy.

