# 6. Vertical transmission risk and outcomes: basic statistical outputs

Basic analyses, without attempts to correct for sensitivity, specificity and cross-reactivity, and making only the simplest assumptions about test persistence, are set out as a series of table shells. The most likely trimester of maternal infection in these tables would be derived from rules based on dates of tests and assumptions about test persistence.

Table 1 provides crude estimates of the risk of vertical transmission and the risk of congenital anomalies, by most likely trimester of presumed maternal infection, and by symptoms.

Table 2 provides a simple listing of congenital anomalies.

Table 3 is a breakdown of outcomes of pregnancy (fetal death, stillbirth) by indicators of maternal infection in pregnancy.

Table 4 represents a generic form of analysis for delivery data and subsequent pediatric outcomes, separate for ZIKV, DENV, and CHIKV, and by trimester of infection, and laid out by birth cohort (Vertically infected, Maternal Infection but no vertical infection, No maternal infection). Covariates can be taken into account by multiple regression.

With so many outcomes to examine, in three distinct diseases, the Table 3 and Table 4 analyses must be considered as hypothesis-forming, not hypothesis-testing.

Tables 1-4 will be computed with standard software, such as SAS, STATA, or R. However, as pointed out in Section 5, any analyses involving the denominator for vertical infection, so especially Table 1 estimates, will be vulnerable to very considerable biases due to inaccuracy in identifying the timing of maternal infection, and indeed, whether there was a maternal infection during pregnancy at all.

The methods set out in the next section are designed to solve these problems, leading to gestational age at infection being represented as *probabilities* that infection occurred in the 1st, 2nd, and 3rd trimester, rather than the usual 0,1 "dummy covariates" used in conventional analyses of gestational age as a risk factor.

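### The all-or-none scenarios for loss to follow-up bound the risk within a birth cohort, but not the contrast between cohorts

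*SAP*

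**What the plan says.** Section 10.2 item 4 sets the main handling: "For categorical pediatric outcomes, survival analyses will treat loss to follow-up as censored observations". It then plans sensitivity analyses for informative loss, and describes their limits in these words: "including examination of the most extreme assumptions, in which (a) all, or (b) no, censored observations are assumed to reach the endpoint". The text does not say whether the assumption may differ between cohorts, and (a) and (b) are the only scenarios named. Item 3 of the same section states: "Loss to follow-up will be carefully monitored and tabulated in relation to infection status".

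Comparisons between cohorts are part of the plan. Section 2.1 requires the effect of maternal infection on pediatric outcomes to be studied both with and without in utero transmission. Section 5.2 explains why there is a second "control group, of children born to mothers with no infection in pregnancy": infection might clear and leave no laboratory markers, or might harm the fetus without crossing the placenta. Section 3.1 defines the three birth cohorts as vertically infected (VI), maternal infection without vertical infection (MI-No VI), and no maternal infection (No MI). Section 6 and Table 4 lay pediatric outcomes out by these cohorts. Section 6 also calls the Table 3 and Table 4 analyses hypothesis-forming.

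**The concern.** What counts as most extreme depends on the quantity being estimated. For the risk in one cohort, the limits are that all, or none, of the lost children reach the endpoint. For a difference or ratio between two cohorts, the limits come from pushing the cohorts in opposite directions. Item 4 gives its label to the first pair without saying that it does not serve the second purpose.

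The MI-No VI against No MI contrast is where this matters most. If the observed risks are about equal and loss is about equal, both planned scenarios return a difference near zero whatever happened to the children who were lost. A report could then say that the absence of an effect survived the most extreme assumptions, although no assumption that could have challenged it was tried. Item 3 shows that the plan foresees loss differing by infection status. Item 4 does not carry this through to what is assumed about the lost children.

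**Working it through.** The SAP gives no figure to reproduce and states neither risks nor loss rates. All rates below are assumptions chosen for illustration.

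**Formulas.** Let p be the observed risk among children followed and L the fraction lost, with subscript 1 for the exposed cohort and 0 for the control cohort. Partial follow-up before censoring is ignored.

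- Cohort risk if none of the lost reach the endpoint: (1−L)p
- Cohort risk if all of the lost reach it: (1−L)p + L
- Risk difference (RD), none in both (scenario b): (1−L1)p1 − (1−L0)p0
- RD, all in both (scenario a): the RD under (b), plus (L1−L0)
- RD, exposed all and control none: the RD under (b), plus L1
- RD, exposed none and control all: the RD under (b), minus L0

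If L1 = L0 = L, scenarios (a) and (b) both reduce to (1−L)(p1−p0), which always has the sign of the observed difference. The crossed pair always spans L1+L0.

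**Equal loss.** Take p1 = 20%, p0 = 5% and L = 20%.

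- Exposed: none gives 0.8×20 = 16%; all gives 16+20 = 36%.
- Control: none gives 0.8×5 = 4%; all gives 4+20 = 24%.
- (a) 36−24 = 12 points; (b) 16−4 = 12 points.
- Crossed: 36−4 = +32 points; 16−24 = −8 points.

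**Null contrast.** Take p1 = p0 = 5% and L = 20%. Each cohort is 4% (none) or 24% (all). Scenarios (a) and (b) both give an RD of 0 and a ratio of 1. The crossed assumptions give 24−4 = +20 and 4−24 = −20 points.

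**Unequal loss, and summary** (RD in points):

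| Observed risks | Lost, exposed / control | (a) all in both | (b) none in both | Exposed all, control none | Exposed none, control all |
|---|---|---|---|---|---|
| 20% v 5% | 20% / 20% | 12.0 | 12.0 | +32.0 | −8.0 |
| 20% v 5% | 25% / 15% | 20.75 | 10.75 | +35.75 | −4.25 |
| 20% v 5% | 10% / 30% | −5.5 | 14.5 | +24.5 | −15.5 |
| 5% v 5% | 20% / 20% | 0 | 0 | +20.0 | −20.0 |

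For the third row: exposed all is 0.9×20+10 = 28% and none is 18%; control all is 0.7×5+30 = 33.5% and none is 3.5%. With unequal loss, (a) and (b) differ by L1−L0 and the sign can change. In every row the planned pair still lies inside the crossed pair.

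**Ratio scale.** In the first row the observed ratio is 20/5 = 4.0. It stays at 16/4 = 4.0 under (b) and falls to 36/24 = 1.5 under (a). At equal loss it cannot cross 1. The crossed assumptions give 36/4 = 9.0 and 16/24 = 0.67.

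**The case against.** The strongest reply has five parts.

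1. **The planned check can show an influence of loss.** A reader might infer from the equal-loss result that it never can. The SAP does not support that. Item 4 concerns survival analyses, which usually report ratios, and under (a) the ratio falls from 4.0 to 1.5 even at equal loss. With 10% and 30% lost, (a) reverses the sign of the difference. This stands. The identical-result problem belongs to the risk difference at equal, or nearly equal, loss, and to null contrasts at equal loss.
2. **Some informative loss is already covered.** A reader might also think that neither scenario represents affected VI children staying in care while well controls leave. In that case no lost child in either cohort reaches the endpoint, which is scenario (b). This stands too.
3. **The text is open.** Item 4 does not say that one assumption must apply to all cohorts, and its list is introduced as non-exhaustive. That is fair, but no opposed scenario is named, and the label suggests that nothing wider exists.
4. **The missing bounds may be derivable.** If (a) and (b) are reported for each cohort, the unadjusted crossed bounds follow from those four numbers. This is true for crude risks. Model-adjusted contrasts need separate runs, and the SAP commits to neither.
5. **The stakes are modest.** One of the two fundamental outcomes in Section 10.4 is the risk of serious outcome given vertical transmission. That is a within-cohort risk, for which all or none are the right outer bounds. Section 6 labels the Table 3 and Table 4 comparisons hypothesis-forming. This limits the impact, but the label does not make a same-direction pair of scenarios a bound on bias.

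**Conclusion.** The point holds for contrasts between birth cohorts and only for those. Scenarios (a) and (b) are valid outer bounds for absolute risk in a cohort. They are not the most extreme assumptions for VI, MI-No VI and No MI comparisons. At equal loss they yield one risk difference twice, and its sign cannot change. In the illustration this is 12 points both times, against −8 to +32 under crossed assumptions; for a null contrast it is 0 both times, against −20 to +20. At unequal loss the planned results do move, by L1−L0 on the difference scale, but still fall short of the crossed bounds.

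The sizes rest on assumed risks and loss rates and on a simple-proportion calculation; the algebra does not depend on the values chosen. The conclusion also rests on the natural reading of item 4, that the same assumption is applied in every cohort. It is a specific correction worth making. Because the comparisons are exploratory, it does not undermine the main analyses.

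**What to change.** In Section 10.2 item 4:

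- Keep (a) and (b), described as bounds on absolute risk within each cohort, and report them by cohort.
- For each between-cohort comparison add (c), in which all censored exposed children and no censored control children reach the endpoint, and (d), the reverse. For contrasts, use the term most extreme only for (c) and (d).
- Because (c) and (d) are wide by construction (40 points apart at 20% loss in each cohort), add an intermediate tipping-point grid in which the assumed risk or hazard after censoring differs by cohort.

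The grid keeps the result interpretable. Let q1 and q0 be the assumed risks among the lost. In the 20% v 5% example with 20% lost from each, RD = 12 + 20(q1−q0) points, so the sign changes only if q0 exceeds q1 by 12/20 = 60 percentage points. In the null example RD = 20(q1−q0) points, so a 20-point gap between lost exposed and lost control children produces a 4-point difference. Readers can judge such gaps for plausibility.

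The cost is one or two sentences in the SAP and a few further runs on the same dataset. The downside is a wider reported sensitivity range.

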#### 10.3 Sample size

No formal sample size calculations have been carried out. The relevant size metric for the VT study is the number of women who are infected in pregnancy, rather than the numbers of women to be followed through pregnancy. A general *initial* target number of women infected in pregnancy, to allow reasonable estimates of vertical transmission rate and the risk of severe clinical outcomes, would be approximately 1000.

Currently there is no clear consensus regarding either vertical transmission rates or rates of congenital damage, and differences between centers cannot be ruled out. It would therefore be a further advantage if recruitment could be spread over 6 or more centers, perhaps varying in intensity of ZIKV infection, and/or in DENV incidence and seroprevalence.

Once, say, 600 ZIKV infections in pregnancy have been followed through to ascertainment of vertical infection, sample size should be reviewed, depending on the transmission risk and risk of severe outcomes, and taking into account other analyses that have appeared at that time or are planned. At that point, fresh consideration could be given to the eventual size of the study, and the potential advantages of targeted recruitment of women with specific risk factors.

#### 10.4 Multiplicity

ZIKA-VT is built around two fundamental, pre-specified, and semi-independent outcomes: vertical transmission rate, and the risk of serious adverse clinical outcomes conditional on vertical transmission. Risk factors have also been pre-specified, based on risk factors that are important in other congenital infections

All other outcomes will be considered under the heading of hypothesis formation rather than hypothesis testing. No special measures will be taken for multiple outcomes, although Bonferroni adjustments may be applied to significance tests.

Author: [name] (UNIVBRIS)

32

#### 10.5 Interim analyses

Estimates of the key parameters can and should be updated at any time as new data is accumulated, without the need for statistical adjustment. This is an observational study which broadly follows local standard of care, with some additional arbovirus testing in certain groups. Therefore, no "stopping rules" will be applied.

#### **TABLES**

#### Table 1: Risks of Vertical Transmission and Congenital malformation.

#### **Definitions:**

- 1. Presumed maternal infection based on PCR+, IgM+, Seroconversion or rising IgG titer
- 2. Trimester, most likely trimester based on test dates and persistence
- 3. Vertical infection based on IgM+, PCR+ in cord or sample from newborn < 7days old, or persistent antibody.
- 4. Severe and mild congenital malformation, to be defined

	Trimester of presumed infection	Symptoms during pregnancy	Number of Mothers infected	Number Vertically infected	Number of Congenital malformations (severe)	Number of Congenital malformations (mild)
	1	Yes				
		No				
ZIKV	2	Yes				
		No				
	3	Yes				
		No				
	1	Yes				
		No				
DENV	2	Yes				
		No				
	3	Yes				
		No				
	1	Yes				
		No				
CHIKV	2	Yes				
		No				
	3	Yes				
		No				

Author: [name] (UNIVBRIS)

34

## Table 2. Listing of all congenital anomalies at delivery

#### Including:

Most likely trimester of maternal infection
Ultrasound findings
Outcome of pregnancy: fetal death, stillbirth, livebirth
Gestational age at delivery (GA)
Birthweight, birthweight for GA, head circumference, head circumference for GA.
Description of anomalies at delivery: cranial morphology; brain anomalies; congenital contractures; neurological sequelae.

Author: [name] (UNIVBRIS)

Table 3. Outcomes of pregnancy: generic summary tables and covariate analyses

- Individed	- .	1		T					
	Trimester	Symptoms	Number of						
	of	during	Mothers in						
	presumed	pregnancy	category						
	infection	,,							
	1	Yes							
Monthoul		No		Outcomes of pregnancy to be					
Vertical	2	Yes		tabulated.					
infection		No		-					
ZIKV	3	Yes							
		No		Abnormal ultrasound findings					
	1	Yes		Abnormal ultrasound findings:					
Vertical		No		specific abnormalities, groups of					
Infection	2	Yes		abnormalities, etc. to be tabulated					
DENV		No		Fetal deaths (1 st and 2 nd trimester)					
	3	Yes		Fetal deaths (3 rd trimester)					
		No		Livebirths					
	1	Yes							
		No		Covariates to be considered for					
Vertical	2	Yes		regression analysis Centre					
Infection		No							
CHIKV	3	Yes		Year - season					
		No		Co-infections in the mother					
Maternal	1	Yes							
infection		No		Previous infection in mother, same or					
NO vertical	2	Yes		different arbovirus					
infection		No		Maternal age					
ZIKV	3	Yes		Obstetric history (e.g. previous stillbirth,					
		No		congenital abnormalities)					
Maternal	1	Yes		Comorbidities (e.g. sickle cell, diabetes)					
infection	_	No		Smoking /alcohol /drug use					
NO vertical	2	Yes		SES markers					
infection	_	No							
DENV	3	Yes							
	3	No							
Maternal	1	Yes							
infection	_	163							
NO vertical		No		1					
infection		140							
CHIKV	2	Yes		1					
J	_	No		1					
	3	Yes		1					
	3			1					
		No	1						

Author: [name] (UNIVBRIS)

Table 4. Outcomes by birth cohort: generic summary tables and covariate analyses

	Trimester of	Symptoms during	Number of Mothers	Outcome	Outcomes to be tabulated:
	presumed infection	pregnancy	in category		Number (%) preterm <37 completed weeks
	1	Yes			Gestational age (mean, sd)
		No			Number (%) livebirths
Vertical	2	Yes			Number (%) neonatal deaths
infection		No			Number (%) deaths at one year
ZIKV	3	Yes			Birthweight (mean, sd)
		No			Birthweight for GA (mean, sd)
	1	Yes			Length (mean, sd)
Vertical		No			Length for GA (mean, sd)
Infection	2	Yes			Head Circumference (mean, sd)
DENV		No			Number (%) SGA
	3	Yes			Head Circumference for GA
		No			(mean, sd)
	1	Yes			Number (%) severe congenital
		No			Number (%) severe congenital malformations on delivery
Vertical	2	Yes			Number (%) mild congenital
Infection		No			malformations at delivery Number
CHIKV	3	Yes			(%) severe clinical outcomes at 1 year
		No			Number (%) mild clinical outcomes at
Maternal	1	Yes			1 year
infection		No			Number (%) auditory problems
NO vertical	2	Yes			Number (%) Ophthalmological
infection		No			problems
ZIKV	3	Yes			
		No			Weight, height, head circumference:
Maternal	1	Yes			at 6m, 12m, 24m (mean, sd)
infection		No			
NO vertical	2	Yes			Developmental findings at 6m, 12m,
infection		No			24m
DENV	3	Yes			etc.
		No			
Maternal	1	Yes			Covariates to be considered for
infection		No			regression analysis
NO vertical	2	Yes			Centre
infection		No			Year - season  Co-infections in the mother
CHIKV	3	Yes			
		No			Previous arbovirus infection in mother, same or different arbovirus.
No Evidence of maternal		Yes			inother, same of unferent arbovirus.
infection					

37

Author: [name] (UNIVBRIS)

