#### 7.2 Risk of severe outcomes of congenital infection

A similar form of analysis will be carried out for severe outcomes of congenital infection. The precise definition remains to be determined, but could include: fetal death, stillbirth, microcephaly, cranial disproportion, or ZIKV-related death within the first two years. The analysis will estimate the risk of severe outcomes conditional on vertical transmission having taken place. This clarifies that there may be two distinct processes: risk factors for congenital infection, and risk factors for severe damage given congenital infection.

The form of analysis for severe clinical outcomes conditional on vertical infection parallels that for vertical transmission rate. Here,  $c_i$  is the risk of severe outcomes in a child born to women i, and C(t) is the probability of severe outcomes given maternal infection in week t. Data  $Z_i=0,1$  indicating severe (1) or non-severe (0) outcomes is a Bernoulli realization of  $c_i$ , and can be used to update C(t) and  $\pi_i(t)$ :

$$c_i = \sum_t C(t)\pi_i(t), \quad Z_i \sim Bern(c_i)$$

Author: [name] (UNIVBRIS)

19

The analysis can be extended to include risk factors as shown above.

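### Table 4 gives weight, height and head circumference at 6, 12 and 24 months only as unstandardised means and SDs, and no line or fixed definition ensures that microcephaly developing after birth is counted

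*SAP*

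**What the plan says.** Table 4 of the SAP (outcomes by birth cohort) lists the post-natal growth measures as "Weight, height, head circumference", summarised "at 6m, 12m, 24m (mean, sd"). No age- or sex-standardised version is listed.

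Size at birth is handled differently in the same table. Weight, length and head circumference each appear raw and again relative to gestational age, for example "Birthweight for GA (mean, sd") and "Head Circumference for GA". Small-for-gestational-age births are counted. Preterm delivery has its own line, "Number (%) preterm <37 completed weeks".

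The covariates legible in Table 4 are centre, year and season, maternal co-infections and "Previous arbovirus infection in mother, same or different arbovirus". Section 6 adds: "Covariates can be taken into account by multiple regression".

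On microcephaly, Section 7.2 says the severe outcome is still to be defined but could include "fetal death, stillbirth, microcephaly, cranial disproportion, or ZIKV-related death within the first two years". Table 4 also counts severe and mild clinical outcomes at one year, without defining them. Objective 2.1(c) asks for the frequency, type and severity of paediatric adverse outcomes, growth among them, up to 2 to 4 years of age.

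**The concern.** The authors evidently accept that raw size is not enough at birth, because they add a version relative to gestational age. That protection stops after birth, although size at 6, 12 and 24 months depends on exact age, sex and gestation at delivery. The regression that Section 6 allows does not help as listed, since none of those three is among Table 4's covariates.

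Two things are at stake. First, a difference between cohorts in mean head size could partly reflect sex mix, visit timing or prematurity, or such differences could mask a real effect. Second, a mean and SD answer neither how often growth is abnormal nor how severely, which is what objective 2.1(c) asks. A few children with very small heads barely move a cohort mean.

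**Working it through.** The SAP states no SD, growth rate, effect size or power for growth, and Section 10.3 says no formal sample size calculation was done. There is no figure to reproduce. The textual check comes first, then an illustration in which every input is an assumption.

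**What Table 4 provides**

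| | At birth | At 6, 12, 24 months |
|---|---|---|
| Raw mean and SD | yes | yes |
| Standardised measure | relative to gestational age | none |
| Count of abnormal size | small for gestational age | none |

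The only timed counts of severe and mild post-natal clinical outcomes are at one year.

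**Illustration.** Units are SDs within sex and exact age.

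*Sex.* Assume boys and girls differ by d = 0.5 to 1.0 SD and are mixed 50:50. The raw SD is √(1 + d²/4): √1.0625 = 1.031 for d = 0.5 and √1.25 = 1.118 for d = 1.0. The SD therefore rises by 3% to 12% with no imbalance at all. A 10-point sex imbalance would move the mean by 0.10 × d = 0.05 to 0.10 SD.

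*Prematurity.* Assume preterm children are 0.3 to 1.0 SD smaller at the visit and one cohort has 5 to 20 points more preterm births. The mean moves by 0.05 × 0.3 = 0.015 SD up to 0.20 × 1.0 = 0.20 SD.

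*Affected subgroup.* Assume a fraction p of children is shifted down by s SD. The mean moves by p × s. The share below -2 SD goes from Φ(-2) = 2.3% to (1 - p)Φ(-2) + pΦ(-2 + s). Children needed per group (two-sided 5%, 80% power, 1:1):

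- mean: n = 2(1.960 + 0.842)² / (p × s)², with SD 1
- count: n = [1.960√(2p̄(1 - p̄)) + 0.842√(p₁(1 - p₁) + p₂(1 - p₂))]² / (p₂ - p₁)²

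| p | s | Shift in mean (SD) | Share below -2 SD | n per group, mean | n per group, count |
|---|---|---|---|---|---|
| 2% | 2 | 0.04 | 3.2% | 9,812 | 4,611 |
| 2% | 3 | 0.06 | 3.9% | 4,361 | 1,755 |
| 5% | 2 | 0.10 | 4.7% | 1,570 | 922 |
| 5% | 3 | 0.15 | 6.4% | 698 | 387 |
| 10% | 2 | 0.20 | 7.1% | 393 | 306 |
| 10% | 3 | 0.30 | 10.5% | 175 | 139 |

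For p = 5% and s = 3, the share is 0.95 × 0.0228 + 0.05 × 0.8413 = 0.0637. The count needs 21% (139 against 175) to 60% (1,755 against 4,361) fewer children per group than the mean. The mean column uses SD 1, so it does not charge the mean for the extra variance of unstandardised data.

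On these assumptions, bias from sex or prematurity (0.015 to 0.20 SD) overlaps the shift produced by an affected minority (0.04 to 0.30 SD).

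**The case against.** The strongest reply is that Table 4 is an open shell. Its title calls it generic, its outcome list is left open, its covariates are only for consideration, and Section 6 labels Tables 3 and 4 hypothesis-forming. The covariate list is plainly not exhaustive: Section 2.1 treats socioeconomic and educational variables as potential confounders, yet they are not legible in Table 4. Mean gestation and preterm birth are tabulated by the same cohorts, so an imbalance in prematurity would be visible. Visits share the same nominal ages, and visit windows belong in the protocol. Nothing in the SAP suggests that sex mix differs by maternal infection.

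Much of this stands, and it lowers the weight of the point. It does not repair the line as written. Section 7.7 carries the full model's timing probabilities into analyses along the lines of Tables 3 and 4, so Table 4 is more than a preliminary. The hypothesis-forming label concerns the number of outcomes and diseases, not how each is measured. An open-ended list does not change an item already specified.

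A reader might also infer that post-natal microcephaly is never counted. The SAP does not support that. Section 7.2 names microcephaly as a candidate severe outcome without confining it to birth, Table 4 counts severe outcomes at one year, and Section 10.2 provides survival analyses for categorical paediatric outcomes. Nor does listing preterm birth as an outcome mean that the authors expect cohorts to differ in it.

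**Conclusion.** The point holds as a shortcoming of a stated table line. Post-natal growth is summarised without standardisation, the listed covariates leave out sex, exact age and gestation, and no line or fixed definition ensures that microcephaly arising after birth is counted. None covers 24 months.

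Its size cannot be established from the SAP. Bias arises only if the cohorts differ in sex mix, visit age or gestation; without imbalance, sex and age cost precision only. The dilution of a small subgroup needs no imbalance, and 0.15 SD for 5% of children lying 3 SD low is its illustrative size.

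A reader might go further and infer a large spurious difference. For example, assume head growth of 0.4 to 0.6 cm per month, a within-age SD of 1.3 cm and a 2- to 4-week gap in mean gestation or visit age. That gives 0.4 × 2/4.35 = 0.18 cm (0.14 SD) up to 0.6 × 4/4.35 = 0.55 cm (0.42 SD). The arithmetic is right, but the inputs come from outside the SAP, the growth rate applies only around 6 months, and no such gap is documented. These are not estimates of bias in this study. The point is a worthwhile, low-cost improvement to an exploratory table.

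**What to change.** In Table 4, for the 6, 12 and 24 month rows:

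- add the mean and SD of z-scores for exact age and sex, from one named growth standard;
- show the z-scores both corrected and uncorrected for gestation at birth, because prematurity may lie on the causal path from maternal infection and the uncorrected comparison may then be the total effect;
- add the number and percentage with head circumference below -2 SD and below -3 SD at each visit, by birth cohort;
- keep raw values as a secondary listing.

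The cost is a little extra programming and a few more table rows. Date of birth, visit date, sex and gestation at delivery are ordinary cohort data, so no extra visit or measurement should be needed.
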